13.5. Secondary Objectives

To assess the single efficacy criteria at 3 and 6 months post TBI.

To test ET and qEEG parameters as biomarkers of cognitive dysfunction at 3 and 6 months post TBI.

To test ET and qEEG as treatment monitoring tools at 3 and 6 months post TBI.

To check assay sensitivity for the primary objective (rTMS + CRB versus CRB alone) by comparing CRB alone versus PLC.

To assess the safety of rTMS administrated starting with one month after TBI.

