13.4. Primary Efficacy Criteria

13.4.1. Justification for Multidimensional Approach

In the last 30 years, no TBI trial with a traditional design on neuroprotective agents showed a significant treatment effect in moderate to severe TBI (Maas, Roozenbeek, 2010). Thus, the challenge to demonstrate benefit of a novel treatment concepts in TBI is great, but the rewards are regarded as correspondingly high (Maas, Roozenbeek, 2010).

Almost all failed studies used a single measure approach. Nevertheless, outcome after TBI is by definition multidimensional, including neurophysical disabilities, disturbances in mental functioning (e.g., cognitive and executive functioning), and consequential problems in social reintegration.

Thus, in agreement with current recommendations, a multidimensional approach for outcome assessment and classification will be chosen for the present study.

An ensemble of appropriate single efficacy criteria shall be tested by a multivariate, directional test approach, reflecting the "global status of patients in TBI" (Bagiella, 2010), while simultaneously combining two points in time in the sense of a 'repeated measures design'.

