13.4.2. Defined Efficacy Ensemble

The following ensemble of appropriate single efficacy criteria shall be tested by a multivariate, directional test approach, reflecting the global status of patients in TBI after 3 and 6 months:

Multivariate Efficacy Ensemble

- 1. Processing Speed Index, Changes from Baseline, LPCF, ITT
- 2. Stroop Color-Word Test, Changes from Baseline, LPCF, ITT
- 3. Trail Making Test, Changes from Baseline, LPCF, ITT
- 4. Digit Span, Changes from Baseline, LPCF, ITT
- 5. Montreal Cognitive Assessment, Changes from Baseline, LPCF, ITT
- 6. Stockings of Cambridge (CANTAB), Changes from Baseline, LPCF, ITT
- 7. Reaction Time (CANTAB) , Changes from Baseline, LPCF, ITT
- 8. Hamilton Rating Scale for Depression, Changes from Baseline, LPCF, ITT
- 9. Hamilton Anxiety Rating Scale, Changes from Baseline, LPCF, ITT

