13.7. Level of Significance

The multiple level alpha is set to α = 0.05, one-sided, according to current recommendations for randomized phase II trials (Rubinstein 2009; Sumithra 2010; Manish 2011).

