13.9. Sample Size Calculation

The power for this study is determined based on the following design specifications:

- (a) One-sided type I error defined as alpha = 0.05 (multiple level alpha, see section 13.7)
- (b) Type II error defined as $\beta = 0.2$ (Testpower 80%)
- (c) Design alternative effect size: Mann-Whitney statistic (MW) = 0.64 (medium-sized difference according to Cohen (Colditz, 1988); assuming a normal distribution the effect size MW may easily be re-expressed as the well-known Cohen effect size (Cohen, 1988) of a standardized difference (Cohen's d): MW = 0.64 means Cohen's d = 0.5)
- (d) Estimated correlations among the single outcome scales included in the global statistics $\rho = 0.4$)

Nonparametric sample size calculations within the framework of a multiple outcome approach (Wei-Lachin procedure- Wei and Lachin, 1984; Lachin 1992) was performed applying the validated software Nnpar 1.0 from idv Data Analysis and Study Planning, Krailling/Munich (see also Tang, 1989; Lachin, 1981). A good example for sample size calculation according to the Lachin approach (Wei and Lachin, 1984; Lachin 1992; Lachin, 1981) in multidimensional trials with neuroprotective agents is also given by Huang (2008).

Please note: further details of the effect size (Mann-Whitney statistic) are described in section 13.10, further details of sample size assessment are described in the separate document "Sample Size Assessment Based on a Multidimensional Efficacy Approach".

Based on the above design specifications, the total required sample size for the multivariate ensemble results in 30 patients per group (including 10% enhancement for usual "ambiguities", e.g., dropouts). With this sample size a "medium-sized" group difference (MW = 0.64) with regard to the multivariate outcome ensemble at month 3 and 6 can be detected with a power of 80%.

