13.4. ANALYSIS OF EFFICACY

Descriptive statistics and graphs will be generated for the ITT population. In addition, nonparametric effect sizes and confidence intervals (Kruskal Wallis and Dunn's pot hoc test) will be provided for all primary and secondary efficacy criteria at all points in time.

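### The assay-sensitivity check (Cerebrolysin alone versus placebo) has no stated criterion, and a non-significant result could not show that the trial was unable to detect an rTMS effect

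*Protocol*

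**What the plan says.** The trial has three arms of 30: CRB + rTMS, CRB + sham rTMS, and placebo + sham rTMS (Protocol synopsis, SAP 6.2). No arm receives rTMS without CRB. The primary comparison is the first arm against the second. The second against the third serves this secondary objective: "To check assay sensitivity for the primary objective (rTMS + CRB versus CRB alone) by comparing CRB alone versus PLC" (Protocol 13.5, with the same objective in the synopsis, Protocol 4.2 and SAP 5.2).

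The documents state no significance level, pass/fail criterion, assumed CRB effect, power or consequence for that check. The only trial-wide level is in Protocol 13.7: "The multiple level alpha is set to α = 0.05, one-sided". Protocol 13.10 frames the primary test as superiority, with a null hypothesis of MW at most 0.50.

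On prior evidence, Protocol 13.4.1 says that over three decades "no TBI trial with a traditional design on neuroprotective agents showed a significant treatment effect in moderate to severe TBI", and it points to the single-measure approach of almost all the failed studies. Protocol 3.1 supports CRB by mechanism. No CRB-versus-placebo effect size appears.

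Protocol 13.10 and 13.11 require Mann-Whitney effect sizes with confidence intervals. SAP 13.4 instead says that "nonparametric effect sizes and confidence intervals (Kruskal Wallis and Dunn's pot hoc test) will be provided for all primary and secondary efficacy criteria".

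**The concern.** Comparing a reference treatment with placebo tells us about a trial's sensitivity only if the reference is expected to work in that setting. The visible text does not establish this for CRB. The comparison uses only the two sham-rTMS arms, so neither the rTMS arm nor the precision of the primary contrast enters it. If CRB does not separate from placebo, the result fits two explanations equally well: the battery could not detect effects, or CRB has little effect.

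The interpretation of the main result is at stake in two ways:

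- A null rTMS result could be put down to lack of assay sensitivity even when its own interval excludes the effect the trial was sized for.
- A positive rTMS result could be qualified by a failed check, although a significant superiority result has already shown that the trial could detect a difference.

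Because no criterion is given, the reading stays open until results are known. That sits badly with the pre-specification promised in Protocol 13.2.

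**Working it through.** **Inputs**

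| Input | Value | Source |
|---|---|---|
| Alpha | 0.05 one-sided | Protocol 13.7; applying it to the check is an assumption |
| Power | 80% | Protocol 13.9 |
| Design effect | "Design alternative effect size: Mann-Whitney statistic (MW) = 0.64" | Protocol 13.9 |
| "Estimated correlations among the single outcome scales included in the global statistics" | 0.4 | Protocol 13.9 |
| Components K | 9 scales (the last is "9. Hamilton Anxiety Rating Scale, Changes from Baseline, LPCF, ITT") at two visits, so 9 or 18 | Protocol 13.4.2; the K used for sizing is not stated |
| Size | "the total required sample size for the multivariate ensemble results in 30 patients per group (including 10% enhancement" | Protocol 13.9 |
| Small effect | MW = 0.56 | Protocol 13.10 benchmarks |

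**1. Reproduce the plan's sample size.** For one outcome, n per group = (z0.95 + z0.80)² / [6 (MW − 0.5)²]. With z0.95 = 1.645 and z0.80 = 0.842 the sum is 2.487, so n = 2.487² ÷ (6 × 0.14²) = 52.6. Averaging K outcomes multiplies this by f = [1 + (K − 1) × 0.4] / K.

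- K = 9: f = 4.2 ÷ 9 = 0.467, n = 24.5, rounded up to 25. Adding 10% gives 28, within 2 of the stated 30.
- K = 18: f = 7.8 ÷ 18 = 0.433, n = 22.8, rounded up to 23. Adding 10% gives 26.

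**2. Standard error of the averaged MW.** SE = √[f / (6n)].

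- Largest value, taken as that implied by exactly 80% power: 0.14 ÷ 2.487 = 0.0563.
- Smallest value, n = 30 and K = 18: √(0.433 ÷ 180) = 0.0491.

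Both sham-rTMS arms have the planned size, so the same SE serves for CRB versus placebo.

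**3. Probability that CRB versus placebo is non-significant**, Φ[1.645 − (MW − 0.5)/SE]:

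| True CRB effect (MW) | SE = 0.0563 | SE = 0.0491 |
|---|---|---|
| 0.50 (none) | 95.0% | 95.0% |
| 0.52 | 90% | 89% |
| 0.56 (small) | 72% | 66% |
| 0.64 (design effect) | 20% | 11% |

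Worked cell: 0.06 ÷ 0.0563 = 1.066; subtracting this from 1.645 leaves 0.579; Φ(0.579) = 0.72. A simulation with 30 per arm, 18 components and correlation 0.4 (3,000 runs) gave 94%, 66% and 10% at MW 0.50, at 0.56 and at 0.64.

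**4. The primary test in the same trials.** Its power at MW 0.64 does not depend on the CRB effect: 80% by design, 86.5% with n = 30 and K = 9, 88.7% with n = 30 and K = 18. The two contrasts share the CRB arm, so their statistics correlate at −0.5. With no CRB effect and rTMS at MW 0.64, the primary is significant and the check is not in 77.9% of trials at 80% power. As a share of positive primary results that is 0.779 ÷ 0.80 = 97%.

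**5. What a null primary shows by itself.** With no rTMS effect, the upper limit of the two-sided 90% interval falls below 0.64 with probability Φ(0.14/SE − 1.645), which is 80% at SE 0.0563 and 89% at SE 0.0491. A simulation with 27 evaluable per arm and an assumed same-scale correlation of 0.7 between visits had a mean SE of 0.052 and gave about 85%. In that simulation, with neither treatment effective, primary and check were both non-significant in 90% of trials.

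**6. If the SAP's adjustment applied.** SAP 12.2 gives Dunn pairwise tests with Bonferroni. Taking three two-sided pairs at overall 0.05 (sidedness is not stated), the critical value is z at 1 minus 0.05 ÷ 6, or 2.394. On the same averaged statistic with 27 to 30 per arm, the check would be non-significant in 99.2% at MW 0.50 and 88-90% at MW 0.56. The failure rate therefore depends on a criterion that the plan does not name.

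**The case against.** The strongest reply is that the documents contain no decision rule. One sentence lists an objective. Nothing makes the primary conclusion conditional on it, and Protocol 13.8 and 13.10 rest that conclusion on the Wei-Lachin test. This stands. A reader might infer that the plan would label the trial insensitive, or overrule a positive rTMS result, when CRB fails to beat placebo. The text does not say so. The one-sided 0.05 criterion used above is an assumption.

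A reader might also take 95% as the failure rate whenever CRB does little. It is 1 minus alpha and applies only at exactly zero effect. At the protocol's own small benchmark the figure is 66-72%.

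Nor does Protocol 13.4.1 show that CRB is ineffective. It concerns traditional designs in moderate to severe TBI and points to single-measure outcomes, whereas the inclusion criteria in Protocol 6.1 are not limited to that severity. The reference list includes a review of neurotrophic treatment in stroke and TBI, and the product information is in an appendix that is not available here. The fair statement is only that the visible text supplies no CRB effect size.

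Finally, the protocol itself already requires Mann-Whitney intervals. The gap in intervals lies in the SAP.

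These points narrow the concern but do not remove it. Blaming past failures on single measures explains the choice of a multivariate test; it does not supply a CRB effect that would make a failed check interpretable.

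**Conclusion.** The concern holds in limited form. A positive CRB-versus-placebo result would support sensitivity. A non-significant one says nothing usable about the trial's ability to detect rTMS, because no CRB effect is established in the visible text and no criterion, level or consequence is set. Under the assumed one-sided 0.05 reading, a non-significant check would be the usual outcome at a zero or small CRB effect, and would still occur in about 11-20% of trials if CRB had the full design effect. The primary test would be adequately powered throughout.

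The ranges rest on correlation 0.4, 9 or 18 components, and precision between that implied by 80% power and that of 30 per arm. The separate sample-size document might fix K, but the conclusion does not depend on it. The validity of the primary test is not in question; what is exposed is how its result will be read. SAP 13.4 adds a distinct error: Kruskal-Wallis and Dunn's test do not yield the Mann-Whitney estimate and interval that the protocol requires.

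**What to change.** - **Synopsis, Protocol 4.2 and 13.5, SAP 5.2:** restate the objective as a secondary estimate of the efficacy of CRB alone versus placebo. Add that a non-significant result will not be used to discount the primary comparison.
- **Protocol 13.10 and SAP 13.4:** interpret a non-significant primary result by its own averaged Mann-Whitney estimate and two-sided 90% interval, which matches one-sided 0.05. If the upper limit is below 0.64, a medium add-on benefit is excluded; otherwise the result is inconclusive.
- **SAP 13.4:** replace the intervals attributed to Kruskal-Wallis and Dunn's test with the Mann-Whitney effect sizes and intervals of Protocol 13.10 and 13.11, for CRB versus placebo as well as for the primary contrast.

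If the sponsor wishes to keep the assay-sensitivity label, the minimum is to justify an expected CRB effect in this population and to state the criterion, the level and what follows from failure.

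The cost is wording in two documents, with no new patients or data. The sponsor gives up the label; the comparison is still made and reported.

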13.6. Secondary Variables

- 1. Eye tracking parameters
- 2. Quantitative EEG parameters
- 3. Safety Parameters (laboratory values, adverse events)

13.7. Level of Significance

The multiple level alpha is set to α = 0.05, one-sided, according to current recommendations for randomized phase II trials (Rubinstein 2009; Sumithra 2010; Manish 2011).

13.8. Multiplicity

Multiplicity regarding multiple primary outcome measures at two points in time is controlled by the chosen correlation-sensitive, multivariate test procedure (Wei-Lachin procedure, see also section 13.10).

13.9. Sample Size Calculation

The power for this study is determined based on the following design specifications:

- (a) One-sided type I error defined as alpha = 0.05 (multiple level alpha, see section 13.7)
- (b) Type II error defined as $\beta = 0.2$ (Testpower 80%)
- (c) Design alternative effect size: Mann-Whitney statistic (MW) = 0.64 (medium-sized difference according to Cohen (Colditz, 1988); assuming a normal distribution the effect size MW may easily be re-expressed as the well-known Cohen effect size (Cohen, 1988) of a standardized difference (Cohen's d): MW = 0.64 means Cohen's d = 0.5)
- (d) Estimated correlations among the single outcome scales included in the global statistics $\rho = 0.4$)

Nonparametric sample size calculations within the framework of a multiple outcome approach (Wei-Lachin procedure- Wei and Lachin, 1984; Lachin 1992) was performed applying the validated software Nnpar 1.0 from idv Data Analysis and Study Planning, Krailling/Munich (see also Tang, 1989; Lachin, 1981). A good example for sample size calculation according to the Lachin approach (Wei and Lachin, 1984; Lachin 1992; Lachin, 1981) in multidimensional trials with neuroprotective agents is also given by Huang (2008).

Please note: further details of the effect size (Mann-Whitney statistic) are described in section 13.10, further details of sample size assessment are described in the separate document "Sample Size Assessment Based on a Multidimensional Efficacy Approach".

Based on the above design specifications, the total required sample size for the multivariate ensemble results in 30 patients per group (including 10% enhancement for usual "ambiguities", e.g., dropouts). With this sample size a "medium-sized" group difference (MW = 0.64) with regard to the multivariate outcome ensemble at month 3 and 6 can be detected with a power of 80%.

13.10. Confirmatory Analyses

Minimizing the required assumptions is a recommended approach for confirmatory statements on efficacy (LaVange, 2005). This applies especially in scales with skewed distributions including floor and ceiling effects as is known from many scales used in TBI. Furthermore, data types can be of different nature (binary, ordinal, continuous). Thus, a non-parametric assessment of treatment effects independent of data type and distribution should be chosen as the primary analysis method.

The analysis will be performed using the Wei-Lachin procedure, a multivariate generalization of the Wilcoxon-Mann-Whitney test, which takes account of the correlation among univariate Mann-Whitney tests for each outcome to produce an overall average estimate of benefit and test for treatment differences. The summarizing test used is, however, not the undirectional or omnibus test of the classical procedure, but instead a directional test which is most efficient in the case of known direction for superiority.

The procedure is described by Wei and Lachin (1984) and Lachin (1992). Practical examples are given in modern textbooks on multiple testing problems(see e.g., Dimitrenko, 2010). Incidentally it should be noted that the nonparametric Wei-Lachin procedure is similar to the frequently used parametric procedure of O'Brien (O'Brien,

Date: 040418

1984). We prefer, however, the Wei-Lachin procedure as it is more robust for practical data sets (minimization of required assumptions (LaVange 2005)) and because the O'Brien procedure has been shown to give too liberal results (Frick 1997).

It is important to note, that the multivariate, directional test procedure chosen for this study can cope simultaneously with binary, ordinal and continuous data. Thus, there is no technical need for the widely used dichotomization of original scales which is associated with substantial loss of information and reflects a major disadvantage of previous TBI studies.

According to the ICH Guideline E9 (ICH Topic E9, Statistical Principles for Clinical Trials, Step 4, Consensus guideline, 5 February 1998, CPMP/ICH/363/96) the results will be given as P-values as well as effect size measures with their confidence intervals (Mann-Whitney statistic as corresponding effects size measure of the Wilcoxon-Mann-Whitney test), so that the direction and quantity of the treatment effects are determined with their precision. The Mann-Whitney statistic is the most valuable effects size measure for the Wilcoxon-Mann-Whitney test because it is appropriate where the Hodges-Lehmann shift parameter is no longer valid. Furthermore, the Mann-Whitney effects size measure is appropriate for continuous, ordinal and binary data at the same time and represents an ideal effects size measure for multiple outcomes. Incidentally, the 25th Anniversary of the journal Statistics in Medicine dedicated a whole issue to papers about the Mann-Whitney statistic (D'Agostino, 2006).

The Mann-Whitney effects size measure (MW) gives the probability that a randomly chosen patient of the test group is better off than a randomly chosen patient of the comparison group, defined in statistical shortcut: P(X < Y) + 0.5 P(X = Y).

Applying the Mann-Whitney effects size measure, the null and alternative hypothesis for the comparisons of the test treatment to control treatment (superiority) can be formulated as follows:

 $\begin{array}{lll} H_0: & MW_{TC} \leq 0.50 \\ \\ H_A: & MW_{TC} > 0.50 \\ \\ H_0: \mbox{ Null-hypothesis; } H_A: \mbox{ Alternative Hypothesis; } T: \mbox{ Test Treatment; } \\ C: \mbox{ Control} \end{array}$

Protocol #: FSNN040418, v1.0 (final) Date: 040418 STUDY ID: CAPTAIN - rTMS

The traditional benchmarks for the Mann-Whitney effects size measure (MW) are as follows (Colditz, 1988):

- 0.29 large inferiority
 0.36 medium inferiority
 0.44 small inferiority
 0.50 equality
 0.56 small superiority
 0.64 medium superiority
- 0.71 large superiority

The confirmatory analyses are performed with the ITT population according to the ICH Guideline E9 (full analysis set). Since the use of the per protocol set, however, maximises the opportunity for a new treatment concept to show additional efficacy in the analysis, and most closely reflects the scientific model underlying the protocol (see ICH E9, section 5.2.2), the supportive analysis by means of the per-protocol set will be regarded as of equal scientific importance (see also Schwartz 1967, Schwartz 1980, Senn 2007).

13.11. Exploratory Analyses

All primary and secondary efficacy criteria will be analyze with descriptive group statistics.

In addition, nonparametric effect sizes and confidence intervals (Mann-Whitney effects size measure) will be provided for all primary and secondary efficacy criteria at all points in time.

Analysis procedures for Eye tracking parameters and Quantitative EEG parameters will be described in the Statistical Analysis Plan.

13.12. Accounting for missing data

13.12.1. Missing Data Problems – General Considerations for a TBI Study

Missing data are a problem in every data analysis. Of course, there are always missing data of the type 'missing completely at random' (MCAR), which in principle will not bias the results; the analysis procedure should be able to cope with partially missing data of such a type. In many studies this type of data is treated by LOCF replacement (Last Observation Carried Forward) as far as there exist follow-up measurements at previous visits.

In a study like the one planned there might also be informatively missing data (missing not at random, MNAR): participants of the study died or are unable to complete the tests because of brain-related impairment. Neglecting these missing data might introduce bias.

A reasonable policy for minimizing bias in the case of informatively missing data (MNAR) is the replacement of these missing data by assigning the worst possible score, or a score worse than those observed. It should be noted that this strategy is only reasonable if rank-based robust procedures are used for the data analysis.

The worst rank imputation procedure was recommended by Lachin in his seminal paper about the missing data problem for data missing because of mortality when performing an exercise test (Lachin, 1999). This procedure was also used when analyzing nonfatal outcomes in studies where mortality was a problem (Lusben, 2002; McMahon, 2001). Recently a similar procedure has been proposed by the 'Traumatic Brain Injury (TBI) Clinical Trials Network' when designing the COBRIT study (Bagiella, 2010).

Temkin (2007) included deaths with the worst rank for the significance tests of neuropsychological scales, but excluded deaths for the calculation of descriptive statistics (e.g., mean, SE estimates). Thus, significance tests reflect all patients with estimation of missing data while the descriptive statistics reflect only the actually observed assessments. We prefer not excluding deaths from descriptive statistics, since the study treatment with more deaths would artificially have better neuropsychological scores while a study treatment preventing deaths would be burdened by rather severe scores of survived patients. The use of robust descriptive statistics in this study allows the inclusion of worst rank scores for deaths also in descriptive analysis. This way, confirmatory analyses and descriptive analysis can be based on the same analysis data and contradictory results are avoided.

